Screening Visit 1b: Once all data (including screening labs) are collected, potential participants will be evaluated for eligibility. If found eligible, participants will have a blood sample drawn (2 mL), collect a self-administered rectal and/or vaginal fluid swab to test for gonorrhea and chlamydia, and provide a urine sample. If the participant tests positive for gonorrhea and/or chlamydia, the participant will be notified and referred for treatment to their primary doctor, health department, or other community STI treatment resources. Study staff will also dispense one dose of each study drug (200 mg of doxycycline and 200 mg of Biktarvy®) at this visit. Staff will provide dosing instructions to participant.

Dosing: Participants will be asked not to eat or drink anything except water after midnight the day before their scheduled dose. Participants will take both study drugs simultaneously at home approximately **1 hour before Visit 2** and will be instructed to take a timestamped photograph or videotape of themselves taking the dose. Photos and videos taken with smartphones automatically include a timestamp. Study staff will instruct participants to bring the photo/video to Visit 2 as proof of dosing. Participants will also have the option to send a text study staff at a specified number at the time of dosing if their phone does not have video/photo capabilities. Participants will be asked to abstain from receptive anal or vaginal sex from the time they take the study drug to 7 days after the biopsy procedure is completed in order to limit additional exposures (e.g. semen, douching, additional lubricants) to the rectal or vaginal mucosa.

Visit 2 (1 hour post-dose): Approximately 18 mL of blood will be drawn. Then participants will provide a urine sample and self- collect rectal or vaginal fluid swab samples.

Visit 3 (2 hours post-dose): Approximately 18 mL of blood will be drawn. Then participants will provide a urine sample and self- collect rectal or vaginal fluid swab samples.

Visit 4 (4 hours post-dose): Approximately 18 mL of blood will be drawn. Then participants will provide a urine sample and self- collect rectal or vaginal fluid swab samples.

Visit 5 (8 hours post-dose): Approximately 18 mL of blood will be drawn. Then participants will provide a urine sample and self- collect rectal or vaginal fluid swab samples.

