Future use of specimens: Leftover biologic specimens will be stored and used for future research use at Emory University Hope Clinic or the CDC. Stored samples will only be distributed to researchers who have obtained protocol approval from an IRB (or appropriate waiver).

8. Sharing of Results with Participants

Study results, including results of laboratory tests and genetic tests, will not be shared with the participants. If abnormalities deemed to be clinically significant are discovered during the

procedure and/or from the safety labs, such as positive chlamydia or gonorrhea tests, these results will be discussed with the participant and a referral will be made to a primary care physician or specialist as needed.

9. Study Timelines

- Participants will be considered on study for no more than 8 weeks.
- The duration anticipated to enroll all study participants is 1 year.
- The estimated date for the investigators to complete this study is 2 years.

10. Inclusion and Exclusion Criteria

Inclusion Criteria

- 1) HIV negative person, who was assigned male or female at birth, who reports sex with another man in the last year and is in good general health
- 2) Aged 18-59 years
- 3) Not currently taking PrEP and no plans to initiate during study
- 4) Not currently taking PEP
- 5) Not currently taking doxycycline or other tetracycline-derived antibiotics and no plans to initiate during the study
- 6) Willing to use condoms consistently for the duration of the study
- 7) Able to provide informed consent in English
- 8) No plans for relocation in the next 4 months
- 9) Willing to undergo peripheral blood, urine, rectal or vaginal secretion collection, and a rectal or vaginal and cervical biopsy procedure
- 10) Willing to use study products as directed
- 11) Hepatitis B surface antigen (HBsAg) negative (screening lab test)
- 12) Creatinine clearance >60 ml/min

Exclusion Criteria

- 1) Currently infected with hepatitis virus and/ or has liver disease
- 2) Current or chronic history of kidney disease or CrCl<60 ml/min
- 3) Continued need for, or use during the 90 days prior to enrollment, of the following medications:
 - a) Systemic immunomodulatory agents
 - b) Supraphysiologic doses of steroids (short course steroids less than 7 days duration, allowable at the discretion of the investigators)
 - c) Chemotherapy or radiation for treatment of malignancy
 - d) Experimental medications, vaccines, or biologicals

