- 4) Intent to use HIV antiretroviral pre/post-exposure prophylaxis (PrEP or PEP) during the study, outside of the study procedures
- 5) Intent to use doxycycline or other tetracycline-derived antibiotics during the course of the study, outside of the study procedures
- 6) Any other clinical condition or prior therapy that, in the opinion of the investigator, would make the patient unsuitable for the study or unable to comply with the study requirements
- 7) Not pregnant and no plans on getting pregnant throughout the duration of the study
- 8) Known allergic reaction to study drugs.
- 9) Significant laboratory abnormalities at baseline visit for rectal biopsies, including but not limited to: a) Hgb ≤ 10 g/dL b) PTT > 1.5x ULN or INR > 1.5x ULN c) Platelet count <100,000

This study will not include any of the vulnerable populations listed below.

- Adults unable to consent
- Individuals who are not yet adults (infants, children, teenagers)
- Pregnant women
- Prisoners

11. Vulnerable Populations

This research will not involve human fetuses, neonates, prisoners, minors or cognitively impaired adults.

12. Local Number of Participants

This study will enroll a total of 20 participants (10 MSM and 10 women) at Emory. In order to enroll all 20 participants, it is anticipated that 40 will sign consent and be screened.

13. Recruitment Methods

[name] and co-investigators have a successful track record in recruiting MSM for their research protocols utilizing all of the recruitment methods detailed below. All recruitment materials will be IRB-approved prior to use.

Databases

The Hope Clinic maintains a large database of people who have previously expressed interest in participating in future research. Additionally, the study team will use existing Emory University databases, including Research Match and the Emory Healthcare Clinical Data Warehouse, who have consented to be contacted about research opportunities.

Email blasts and phone calls will be made to potential participants from these databases.

Face- to-face Engagements

Participants may be actively or passively recruited at community venues listed below and engaged with limited information about the study and study qualifications. A site contact sheet or a tablet using SurveyGizmo will be used to populate name, phone number, and email address of interested participants. Examples of locations used for face-to-face engagement are listed below:

- a. Community annual events attended by study population

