To protect against possible side effects of the study drug, women who are pregnant or nursing a child may not take part in this study. If a female participant becomes pregnant, there may be risks to the participant, the embryo, or fetus. These risks are not yet known. Women of childbearing potential will be asked to provide a urine pregnancy test to ensure they are not pregnant, prior to administering drug. Women of childbearing ability will discuss contraceptive methods to use throughout the study and may be asked to abstain throughout the duration of the study. If the participant becomes pregnant during the study, they must inform the study doctor immediately. Pregnant women will be excluded or removed from the study.

Biktarvy® (TAF/FTC/BIC)

Biktarvy® is a combination anti-HIV medication that contains the drugs tenofovir alafenamide, emtricitabine, and bictegravir. Based on clinical trials previously conducted of Biktarvy®, the drug showed to be well tolerated (see package insert). The most common adverse events reported in clinical trials ($\geq 5\%$ incidence) included diarrhea, nausea, and headache. Additional adverse reactions occurring in less than 2% of subjects administered Biktarvy® included vomiting, flatulence, dyspepsia, abdominal pain, rash, and depression.

Renal toxicity and bone density loss are rarely reported with chronic use of TAF containing products and are not expected to occur with the dose regimen prescribed in this protocol. Similarly, lactic acidosis and severe hepatomegaly have rarely been associated with medications in the same class as TAF and FTC; however, are not expected to occur with this regimen.

Use of TAF/FTC can also cause flare-ups in those who have hepatitis B virus. It can cause the Hepatitis B virus to suddenly return in a worse form than before if treatment was provided (see package insert). For this reason, it is important that participants not participate in the study if they are known to have Hepatitis B. Nonetheless, the maximum 1-day dosing regimen for this study is unlikely to cause flare-ups in Hepatitis B even if not diagnosed.

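### Exclusion criterion 7 is worded as an inclusion criterion, and the bar on nursing women in Section 15 appears in none of the 21 eligibility criteria

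*Combined protocol and SAP*

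**What the plan says.** Section 10 of the protocol has 12 inclusion criteria and 9 exclusion criteria. Exclusion criterion 7 reads "Not pregnant and no plans on getting pregnant throughout the duration of the study".

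Two neighbouring criteria show how the same kind of rule is worded elsewhere in that section. Inclusion criterion 3 reads "Not currently taking PrEP and no plans to initiate during study". Its counterpart, exclusion criterion 4, reads "Intent to use HIV antiretroviral pre/post-exposure prophylaxis (PrEP or PEP) during the study, outside of the study procedures".

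After the criteria, Section 10 adds "This study will not include any of the vulnerable populations listed below", followed by four bullets. One of them names pregnant women; none names nursing women.

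The doxycycline part of Section 15 (Risks to Participants) states that "women who are pregnant or nursing a child may not take part in this study". It also says that pregnant women will be excluded or removed, and asks for a urine pregnancy test before drug is given.

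Three other provisions bear on conception during the study:

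- Inclusion criterion 6: "Willing to use condoms consistently for the duration of the study".
- The Dosing paragraph of Section 6, which asks participants to "abstain from receptive anal or vaginal sex from the time they take the study drug to 7 days after the biopsy procedure is completed".
- Section 15: "Women of childbearing ability will discuss contraceptive methods to use throughout the study".

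**The concern.** There are two defects, both in the section that decides who may be dosed.

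First, criterion 7 has reversed polarity. It describes the person the study wants to enrol but sits in the list of reasons to refuse.

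Second, one sentence in Section 15 bars both pregnancy and nursing, but only pregnancy was carried into Section 10. The nursing rule is left in the text on doxycycline risks.

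Under Section 6, eligibility is assessed and one dose of each drug is dispensed at the same visit, 1b. The participant then takes the dose at home, so this visit is the main gate before exposure. With a single dose, withdrawing someone afterwards does not undo the exposure. Pregnancy has a laboratory test behind it. The protocol text describes no procedure that specifically asks about nursing.

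**Working it through.** No power, alpha or sample-size figure is involved. The check is a count of criteria and a comparison of rules.

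**1. Is criterion 7 out of line with its own list?** Exclusion criteria 1 to 6, 8 and 9 each state a condition that rules a person out, which is 8 of 9. Criterion 7 states a condition that rules a person in, which is 1 of 9. The negative form (not doing something, and no plans to) is that of inclusion criteria 3 and 5. Where those two have counterparts in the exclusion list (criteria 4 and 5), the wording was turned round to an intent to use the drug. Criterion 7 was not turned round. It is complete and numbered in sequence, so this is not a text-extraction fault.

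**2. How far apart are the literal and intended rules?** Let P = pregnant and Q = planning pregnancy.

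- Literal rule: exclude if (not P) and (not Q).
- Intended rule: exclude if P or Q.

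| P | Q | Literal: exclude? | Intended: exclude? | Express bar elsewhere? |
|---|---|---|---|---|
| no | no | yes | no | not needed |
| no | yes | no | yes | none |
| yes | no | no | yes | Sections 10 (bullets) and 15 |
| yes | yes | no | yes | Sections 10 (bullets) and 15 |

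The two rules agree in 0 of 4 rows, because one is the exact negation of the other. The first row is the whole intended population, including all 10 MSM who cannot become pregnant.

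Of the three rows meant to be excluded, two are barred expressly elsewhere. The row for not pregnant but planning pregnancy has no other express bar.

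**3. How exposed is that remaining row?** Three provisions cover it indirectly. Consistent condom use is required for the whole study. The abstinence request runs from dosing to 7 days after the biopsy, which is done at 24 hours:

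24 h + 7 × 24 h = 192 h = day 8 after dosing.

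The last visit is at day 7 (168 h), so the request outlasts follow-up. The contraception discussion adds to this. Conception on study is therefore unlikely even without a working criterion 7.

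**4. Where does nursing appear?**

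| Place | Items | Naming nursing, breastfeeding or lactation |
|---|---|---|
| Section 10, inclusion criteria | 12 | 0 |
| Section 10, exclusion criteria | 9 | 0 |
| Section 10, excluded-populations bullets | 4 | 0 |
| Section 15, doxycycline risks | – | 1 mention, as a fixed rule |

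That is 0 of 12 + 9 = 21 criteria.

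**5. What else could catch a nursing woman before dosing?** Section 5 has the clinician assess medical history before dispensing, but does not mention nursing. Exclusion criterion 6 allows refusal on the investigator's opinion. Both are general or discretionary, whereas Section 15 gives no discretion. Section 14 concerns ending participation, not entry. Its exclusion-criterion bullet would not reach a nursing woman by name, although read literally it would reach every intended participant through criterion 7.

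**The case against.** The best reply is that intent is plain and the protocol binds as a whole. Pregnant women are named as excluded directly below the criteria and again in Section 15, with pregnancy testing behind both. No site would apply criterion 7 literally, since that would stop enrolment altogether. Even inverted, the line prompts a screener to ask about pregnancy plans, and condom use and abstinence cover what remains. On this view the four-row comparison measures a reading that nobody would use. As for nursing, the rule exists and nothing in Section 10 contradicts it, so the complaint is about placement. Finally, the eligibility checklist and pre-screening questionnaire are not in the documents, and consent pages were removed. Nursing may be asked about there.

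Much of this stands. The polarity error is a drafting slip that would very probably correct itself in use, and the risk of a planned pregnancy on study is small. It is also fair that an omission from a working checklist is an assumption, because no checklist can be seen.

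It does not dispose of the point. An operative eligibility rule is wrong as written, and obvious intent is a reason to correct it easily, not a reason to leave it. Obvious intent does not help with nursing either: nothing in Section 10 hints at that rule, so a reader of that section cannot infer it. A question in an unseen form would not repair the protocol's own list.

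**Conclusion.** Both parts hold, and the point is minor. Exclusion criterion 7 is inverted (1 of 9 exclusion criteria; literal and intended rules agree in 0 of 4 cases). The nursing bar is missing from all 21 criteria and from the four bullets that follow, although Section 15 states it as mandatory.

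The nursing omission is the more substantive part, because it is less visible and has no test behind it. It concerns chiefly the planned 10 women among 20 participants, and fewer in practice because that group may include trans women. That figure assumes nobody in the MSM group could be nursing. Inclusion criterion 1 is worded by sex assigned at birth and does not strictly rule this out.

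The wording and the counts are certain. The practical consequence rests on the assumption that sites screen from Section 10 and that no unseen form asks about nursing. No endpoint, analysis or sample-size figure changes.

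**What to change.** Replace exclusion criterion 7 with: *Pregnant, nursing, or planning to become pregnant during the study.* This restores the polarity, keeps the bar on planned pregnancy, and puts the nursing rule where eligibility is decided. It uses only rules the protocol already states or plainly intends. If a screening checklist or pre-screening questionnaire was built from Section 10, check that it matches.

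The cost is one reworded line at the next protocol amendment, with no added test, visit or participant.

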Doxycycline (DOX [200 mg]) is an oral medication used to treat or prevent infections that are strongly suspected to be caused by bacteria; it is an antimicrobial drug indicated for bacterial infections such as sexually transmitted infections.

Biktarvy

Biktarvy® (200mg) is an oral combination anti-HIV medication that contains the drugs tenofovir alafenamide, emtricitabine, and bictegravir.

Both study drugs will be stored and dispensed per manufacturer instructions by the Emory Investigational Drug Services Pharmacy Satellite location at the Hope Clinic. Prior to drug dispensing, the clinician will assess participant's medical history, and ensure the participant has no known allergies to the study drug. If a participant reports an allergy and a suitable alternative is not available, then the clinician may opt to not enroll the participant into the study.

6. Procedures Involved

When possible, study activities such as questionnaires will be done remotely due to the ongoing COVID-19 pandemic.

Phone Screening (if applicable): Potential participants may be identified from Hope Clinic databases of former study participants or self-referrals after seeing study flyers, social media ads, etc. In these cases, study staff will administer a pre-screening questionnaire via phone to assess preliminary eligibility. If the results of the pre-screening questionnaire indicate that the potential participant may be eligible for this study, they will be invited to the clinic to complete the first screening visit.

Screening Visit 1a: Potential participants will be asked about their medical history, undergo a physical exam, and have a peripheral blood sample drawn (17.2 mL) for lab tests (creatinine, complete blood count, coagulation, HIV and Hepatitis B) and research tests (baseline levels of study drug). A pregnancy test will also be performed on women of childbearing potential.

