All vaginal and cervical biopsies will be completed using a speculum by experienced, trained clinicians. All biopsy procedures will be performed in an examination room at the Hope Clinic with assistance from the project coordinator or clinical research nurse. Similar procedures have been performed in other research protocols conducted at the Hope Clinic with no complications. A pelvic exam will be done prior to all vaginal and cervical biopsies to make sure it is safe to collect vaginal and cervical tissue samples. Up to two adequate ~2.4 mm thick biopsy specimens will be taken from normal-appearing vaginal mucosa using a sterilized mini tischler biopsy forceps. All biopsy specimens will be coded with a unique numeric identifier such that the CDC laboratories that receive the specimens will be unable to link them back to the study participants. Specimens will be transported directly to CDC after the study visit.

Twenty-four to forty-eight hours after the procedure, or the next study visit, whichever comes first, study personnel will contact the subjects who donated vaginal cervical biopsy samples and inquire about symptoms, complications, or adverse events related to study procedures. Subjects who report symptoms suggestive of any significant complications will receive advice on seeking care and will be given referrals to appropriate healthcare professionals as needed. This follow-up may be completed over the phone or through electronic communication.

PrEP Linkage

Participants will also be educated about HIV pre-exposure prophylaxis throughout the study by trained study staff. After completion of the study, all participants who qualify and are interested in PrEP for HIV prevention will be linked to community services. A detailed listing of PrEP services available for insured and uninsured clients in Atlanta can be found at www.prelocator.org. [name] is active in PrEP implementation in the Atlanta community and can facilitate these linkages.

7. Data and Specimen Banking

Data collected for this study will be analyzed and stored at the Hope Clinic. After the study is completed, the de-identified, archived data may be stored for use by the researchers at the Hope Clinic and collaborative partners at The Centers for Disease Control and Prevention.

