As with rectal biopsies, there are risk associated with cervical and vaginal biopsies. These risks include pain, discomfort, a persistent odor, bleeding, and infection. If bleeding occurs that cannot be stopped by applying pressure, medication will be used, such as monsel's solution and paste, to stop it. Silver nitrate has a gray color that can cause gray flecks in the vaginal discharge after the biopsy is completed. All female participants will be notified of this expected side effect.

A delegated, licensed medical professional who has trained in the procedure will complete all biopsies.

To minimize some of these risks, study staff will limit the collection to a maximum of two vaginal and two cervical samples. Study subjects will be instructed to take over-the-counter pain medication before and/or after the procedure, such as Tylenol, if not contraindicated. Subjects will be instructed on how to care for the area and to contact the PI or their medical care provider if any of the aforementioned risk occur and persist.

The procedure is not anticipated to be associated with any deleterious impact on participants' health or well-being.

Doxycycline

Doxycycline (DOX) is a medication used to treat or prevent infections that are strongly suspected to be caused by bacteria. DOX is an antimicrobial drug indicated for bacteria infections such as sexually transmitted infections. The most common adverse reaction reported is diarrhea. Other adverse reactions include vomiting, nausea, dysphagia, and inflammatory lesions. Additional adverse reactions that are rare and not expected to occur with a one-dose regimen prescribed in this protocol include hepatotoxicity, exfoliative dermatitis (skin), rise in BUN levels, hypersensitivity reactions, hemolytic anemia, neutropenia, and eosinophilia.

The medication provided in this study is not for treatment or prevention of HIV and other STI infections. Participants who are interested in pre-exposure prophylaxis (PrEP) after this study ends, will be referred to a medical provider who can prescribe PrEP.

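### Exclusion 9 states its haemoglobin, clotting and platelet limits only for rectal biopsies, so a woman having only vaginal and cervical biopsies meets no stated limit of that kind

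*Combined protocol and SAP*

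**What the plan says.** **The limits.** Exclusion 9 (Section 10) begins "Significant laboratory abnormalities at baseline visit for rectal biopsies, including but not limited to" and lists haemoglobin of 10 g/dL or less, PTT or INR above 1.5 times the upper limit of normal, and platelets below 100,000.

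**Who has which biopsy.** Under Visit 6 (Section 6), participants with a vagina have vaginal and cervical biopsies, and all others have a rectal biopsy. Those who have the vaginal biopsy may also choose a rectal one at the same visit.

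**Which tests are drawn.** Screening Visit 1a takes blood from all potential participants for "lab tests (creatinine, complete blood count, coagulation, HIV and Hepatitis B"). At Visit 1b, eligibility is judged once the screening results are in, and the study drugs are then dispensed.

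**What is said about the vaginal and cervical procedure.**
- Section 15 says of it: "These risks include pain, discomfort, a persistent odor, bleeding, and infection". It adds: "If bleeding occurs that cannot be stopped by applying pressure, medication will be used". It also caps the sampling: "study staff will limit the collection to a maximum of two vaginal and two cervical samples".
- Section 6 provides for an examination beforehand: "A pelvic exam will be done prior to all vaginal and cervical biopsies to make sure it is safe to collect" tissue. Afterwards, at 24 to 48 hours or at the next visit if sooner, "study personnel will contact the subjects who donated vaginal cervical biopsy samples and inquire about symptoms, complications, or adverse events".
- Visit 6 bars vaginal and cervical sampling during menstruation, pregnancy or possible infection.

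**The concern.** The protocol orders a blood count and clotting tests on every potential participant and sets numeric limits for acting on them, but ties those limits to one biopsy site. Bleeding is a named risk at the other site too. Followed as written, a woman with, say, platelets below 100,000 who will have only vaginal and cervical biopsies fails no blood-count or clotting criterion. The same result would exclude a participant due for rectal biopsy.

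What is at stake is participant safety in a study from which, by Section 16, no direct benefit is expected, together with consistent eligibility decisions. Two members of staff could read the criterion differently and decide differently about the same woman. No estimate or test in the analysis plan depends on this.

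**Working it through.** No sample-size, power or error-rate figure is involved. The check sets the relevant provisions side by side.

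**1. Does the wording of exclusion 9 reach vaginal and cervical biopsies?** No. The open-ended phrase in the criterion widens the list of abnormalities, not the list of biopsy sites. The only site named is rectal.

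**2. Is such a limit stated anywhere else?** The other sections that could hold one are these:

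| Provision | Applies to a woman having only vaginal and cervical biopsies? | Sets a haemoglobin, clotting or platelet limit? |
|---|---|---|
| Inclusion 1, good general health | Yes | No |
| Inclusion 11, HBsAg negative | Yes | No, a different laboratory limit |
| Inclusion 12 and exclusion 2, creatinine clearance | Yes | No, a different laboratory limit |
| Exclusion 1, hepatitis infection or liver disease | Yes | No |
| Exclusion 3, recent immunomodulators, high-dose steroids, chemotherapy or radiation | Yes | No |
| Exclusion 6, investigator opinion | Yes | No |
| Visit 1a, blood count and coagulation drawn | Yes | No, tests only |
| Visit 6, no sampling during menstruation, pregnancy or possible infection | Yes | No |
| Section 6, pelvic examination before biopsy | Yes | No |
| Section 15, pressure and then medication for bleeding | Yes | No |
| Section 6, follow-up contact after biopsy | Yes | No |
| Section 14, termination for a laboratory abnormality on best-interest grounds | Yes | No |
| Section 14, termination on meeting an exclusion criterion | Yes, but it only enforces the criteria in Section 10 | No |

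No row supplies the missing limit.

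**3. How many participants could be concerned?** Inputs: 10 women among 20 participants (Section 12); rectal biopsy for everyone without a vagina and optional for the rest (Visit 6).

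Number concerned = 10 − (women without a vagina) − (women with a vagina who choose rectal biopsy).

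- Upper bound, with both subtracted terms zero: 10 − 0 − 0 = 10, and 10 / 20 = 50%.
- Lower bound, if every woman has a rectal biopsy: 0, or 0%.

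This counts women for whom no such limit is stated. It does not count women with an abnormal result. The documents give no frequency of abnormal results, so that second number cannot be derived.

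**4. Could the limit be applied in time?** Yes. The results come from Visit 1a and are available at the Visit 1b eligibility check, before the drugs are dispensed and before the biopsy at Visit 6.

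**5. What about a woman who chooses the rectal option late?** The documents do not say when she must choose, so it is unclear whether exclusion 9 applies to her at Visit 1b. The Section 14 rule on an exclusion criterion that is newly developed or not previously recognised allows her to be stopped if she chooses rectal biopsy later and breaches a limit. That largely deals with her case, though only after she has been dosed. It does nothing for a woman who never chooses rectal biopsy, because she meets no such criterion.

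**The case against.** **The restriction may be deliberate.** Inclusion 9 names rectal, vaginal and cervical procedures together, so the authors could name all three when they meant all three. Rectal sampling takes up to 12 specimens of about 1.0 mm through a sigmoidoscope. The vaginal and cervical procedure takes far fewer: "Up to two adequate ~2.4 mm thick biopsy specimens will be taken from normal-appearing vaginal mucosa", plus at most two cervical samples. Section 6 also reports no complications in similar vaginal and cervical procedures at the clinic. This stands as a possible explanation, but the protocol does not give it. The specimen comparison is not one-sided either, since the vaginal specimens are thicker.

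**The criterion may be meant for everyone.** It sits in the study-level list and is judged at baseline, so a site might apply it to all. That reading leaves no gap, but the words do not say it, and the change would only bring the text into line with such practice.

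**Other safeguards cover these women.** This is true and narrows the point considerably. Exclusions 1 and 3 plausibly remove some people with poor clotting or low counts, and exclusion 6 lets the investigator refuse anyone. But investigator judgement is equally available for rectal-biopsy participants, and the protocol still set numeric limits for them. A pelvic examination does not measure platelets or INR, and bleeding management and follow-up act during or after the procedure.

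**The documents give no basis for the same limits at the other site.** This stands in part. It is why a stated site-specific limit would be an acceptable answer.

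**Conclusion.** The point holds as a low-severity gap in the wording of an eligibility criterion. For 0 to 10 of the 20 participants (0% to 50%), no haemoglobin, clotting or platelet limit is stated before biopsy, and an abnormal result is left to judgement. The upper bound assumes that all 10 women have a vagina and that all decline the rectal option. The conclusion assumes that exclusion 9 is applied as worded.

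Three stronger readings are tempting and are not supported:

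- *These women have no laboratory criterion, or no protection.* Creatinine clearance, HBsAg and the safeguards listed in the working apply to them.
- *Up to 10 women will be biopsied at unsafe values.* Harm would need a woman to breach a limit and the investigator to enrol her all the same. The documents allow neither to be estimated. Counting planned specimens would not measure that risk either.
- *The study results are affected.* The 24-hour concentration comparisons do not depend on these limits.

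**What to change.** In exclusion 9, change *for rectal biopsies* to *for rectal, vaginal or cervical biopsies*. The blood count and coagulation results from Visit 1a are then judged against the same limits for every participant at Visit 1b, before drug is dispensed. This also removes the doubt about a woman who chooses the rectal option later. If the sponsor intended a site-specific limit, state the vaginal and cervical limit instead, with the reason for the difference.

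The cost is a few words in one criterion, with no new test, visit or analysis. The downside is possibly a few more screen failures among women, a number that the documents do not allow to be estimated. The 40 people expected to be screened (Section 12) should not be taken as room to absorb them, because that is the number thought necessary to enrol 20 under the present criteria.
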